## 4.5.16 Self-efficacy for exercise scale (SESS)

Self-efficacy for exercise scale consists of 9 items scored from 0 (not confident) to 10 (very confident). A total score is calculated by summing the responses to each question, giving a total score from 0-90. A higher score indicates higher self-efficacy for exercise. This score will be analysed using linear regression adjusting for baseline SESS and the same variables as in the primary analysis.

## 4.5.17 Social Support Survey (mMOS)

mMOS Social Support Survey – 8 item includes 8 items on instrumental and emotional subscales. The mMOS-SS is scored as the average score of subscale items transformed to a zero to 100 scale, with higher scores indicating more support. See http://www.rand.org/health/surveys tools/mos/mos socialsupport scoring. html
This score will be analysed using linear regression adjusting for baseline mMOS score and the same variables as in the primary analysis.

## 4.5.18 Social Support for Exercise scale

Social Support for Exercise scale is a 13-item scale with responses on a 5-point Likert scale how often (1, none to 5, very often). An average social support score is calculated for friends, family, and combined friends and family, where higher scores indicate greater social support for physical activity and exercise. The score will be summarised descriptively by intervention arm.

#### 4.5.19 Locus of Causation in Exercise (LCE)

Locus of Causation in Exercise consists of three items, with responses ranging from 1 (strongly disagree) to 7 (strongly agree). To score the LCE, reverse scores on items two and three and then calculate the mean for the three items. High scores indicate greater self-determination or a more internal perceived locus of causality and low scores less self-determination. The score will be analysed using linear regression adjusting for baseline LCE and the same variables as in the primary analysis.

## 4.5.20 Technology Acceptance Model Perceived Ease of Use scale

Technology Acceptance Model Perceived Ease of Use scale consists of six items on a 1 (extremely likely) to 7 (extremely unlikely) Likert scale. The total score is obtained by taking the average score and transforming to a 0 to 100 scale as follows:

PEU = (AVERAGE(TAM07, TAM08, TAM09, TAM10, TAM11, TAM12) - 1)(100/6)

The score will be summarised descriptively by intervention arm.

## 4.5.21 Pedometer use

Pedometer use/purchase will be summarised descriptively by randomised arm.

## 4.6 Additional analyses

## 4.6.1 Subgroup analyses

For the primary outcome at 1 year, exploratory subgroup analyses will be performed by repeating the primary analysis and including a treatment by covariate interaction term for the following baseline subgroups:

Age: above/below 75 years

Gender: male/female

• Deprivation: IMD more deprived (deciles 1-5) vs less deprived (deciles 6-10)

Comorbidities: < 2 vs ≥ 2

Polypharmacy: number of medications ≥ 5 vs ≤ 4

Health diet: high/low prudent diet score (FFQ)

Physical activity: high/low IPAQ score

Depression: depression vs no depression, based on GDS at baseline

Retirement: retired/working

The same subgroups will be analysed in the same way using the primary outcome at 5 years.

## 4.6.2 Sensitivity analyses

- 1. Sensitivity analyses to the primary analysis multiple imputation will include:
  - Delta-based multiple imputation, assuming missing verbal reasoning scores are on average 0.15 points (on a standardised scale) better or worse than the MAR imputed values of verbal reasoning score.
  - complete cases analysis
- 2. Sensitivity analyses for the definition of cognitive impairment will include:
  - MCI defined as 1.5 SD below the norm in another non-memory cognitive domain plus memory impairment.
  - AACD defined as 1 SD below the norm for the Baddeley reasoning test and IADL.
  - Decrements in the other computerised tests (spatial working memory, digital vigilance and verbal short term memory) combined with IQCODE in indicating a diagnosis of dementia.
- 3. A sensitivity analysis to check for any differences resulting from changing the order of the Baddeley verbal reasoning task from the third task to the first task will be also carried out.

## 4.6.3 Further analyses

The health economic analysis plan and the process evaluation plan will be outlined in separate documents. The cognitive and behavioural outcomes at 2, 3, 4 years will be analysed in the process evaluation.

#### 4.7 Safety reporting

For this study Serious Adverse Event (SAE) is defined as any untoward medical occurrence or effect that at any dose:

- · Results in death
- Is life-threatening refers to an event in which the subject was at risk of death at the time of the event; it does not refer to an event which hypothetically might have caused death if it were more severe
- Requires hospitalisation, or prolongation of existing inpatients' hospitalisation
- Results in persistent or significant disability or incapacity
- Other important medical events based upon appropriate medical judgment; they may jeopardise the participant and may require medical or surgical intervention to prevent one of the outcomes listed in this definition.

SAEs will be summarised descriptively by severity and relatedness. No SAEs are considered expected for the purposes of this trial. Occurrence of SAEs among all randomised participants will be analysed using logistic regression.

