# Health economic analysis

The economic evaluation will be taken from an NHS and PSS perspective with a sensitivity analysis from a societal perspective taking employment status into account. The outcome will be expressed as incremental cost per improvement in cognitive functioning scores and per quality adjusted life year gained.

Personal out-of-pocket spending and informal care information will be collected through online questionnaires. We will record all resources required for interventions including staff support time, time using the internet, and the cost of maintaining the LifeGuide platform. Use of relevant primary/secondary care services will be extracted by notes review at years 1 and 5 of the trial. Health-related quality of life (HRQoL) questionnaires will be completed at baseline, and annually from year 1 to year 5. Personal resource usage questionnaires will be completed at years 1 and 5. All relevant resource items identified will be costed using appropriate local or national cost data (e.g. PSSRU, 2007), with informal care costed at the minimum wage level, NHS reference costs, and from participating Trusts where necessary.

EQ5D will be translated to utility score using the UK tariff. Area under the curve approach will be adopted to calculate quality adjust life years (QALYs) and discounted beyond one year for each individual.

We will follow the intention to treat principle. Generalised linear mixed models will be used to estimate the costs and QALYs difference by adjusting baseline characteristics including socioeconomic groups. Where appropriate we will estimate incremental cost-effectiveness ratios. We will estimate mean values and 95% percentiles using non-parametric bootstrapping, and use these to estimate cost-effectiveness acceptability curves. Major assumptions in the costing and analysis will be tested through sensitivity analyses. Missing value will be explored using multiple imputation and presented as sensitivity analyses.

A population dynamic model will be developed to consider prevalence, new incidence, and progression of cognitive impairment, using values informed by our literature review, data collected at feasibility stage and full trial results. We will extrapolate the trial findings to broader settings and test the cost effectiveness implications regarding different take-up rates, intensity of use, and socioeconomic variables.

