### Causality

An SAE occurring to a research participant will be reported to the Active Brains study team where, in the opinion of the Principal Investigator at site, the event was related to administration of any of the research procedures, and was an unexpected occurrence. The causality assessment of the event should always be undertaken by a medically qualified doctor who is delegated to do so as indicated on the trial delegation log.

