### **Expectedness**

For the purposes of this trial no SAEs are considered expected.

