# Non serious AEs and exemptions

- Non-serious AEs will not be collected.
- SAEs NOT DIRECTLY related to the Trial are not required to be reported, this includes deaths and hospital admissions as assessed by PI at site as being not related to the trial website intervention. In such cases deaths will be reported using an End of Study form and will be sent directly to the trial team as per SOP.
- Pre-planned hospitalisation e.g. for pre-existing conditions which have not worsened, elective procedures for a pre-existing condition will not be classed as an SAE unless deemed related to the trial. Hospital admissions that are not directly related to the trial do not need to be reported.

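### SAP 4.7 fits a regression to SAE occurrence in all randomised participants, but the protocol requires reports only of SAEs judged trial-related, so the odds ratio would reflect attribution rather than risk

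*SAP*

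**What the plan says.** **SAP 4.7 (Safety reporting)** defines an SAE without regard to cause. One criterion is "Requires hospitalisation, or prolongation of existing inpatients' hospitalisation". It then plans two outputs: "SAEs will be summarised descriptively by severity and relatedness", and "Occurrence of SAEs among all randomised participants will be analysed using logistic regression". It names no data source, covariates or arm contrast. The contrast has to be taken from SAP 3.5, which compares each active arm with usual care.

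**The protocol's safety sections** define an SAE in the same way but limit what is reported.
- Causality: an SAE goes to the study team where "in the opinion of the Principal Investigator at site, the event was related to administration of any of the research procedures" and where it was unexpected.
- Expectedness: "For the purposes of this trial no SAEs are considered expected", so that second condition removes nothing.
- Non serious AEs and exemptions: "SAEs NOT DIRECTLY related to the Trial are not required to be reported, this includes deaths and hospital admissions". The test for these is the site investigator's view that the event is unrelated to the website intervention. Unrelated deaths go to the trial team on an End of Study form.
- Reporting: practices notify the team of SAEs they consider related.

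**Other sources in the plan** do not depend on relatedness. SAP 4.5.11 analyses death from notes review or from reports by the practice, supporter or relative. For admissions, the protocol's Health economic analysis section says: "Use of relevant primary/secondary care services will be extracted by notes review at years 1 and 5 of the trial". Protocol Table 2 marks mortality and resource use, including hospitalisation, for notes review in the three randomised arms.

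**The concern.** The SAP's two outputs presume a dataset of all SAEs, related and unrelated. The protocol creates a dataset of related SAEs. If the model uses those reports, a participant admitted for a reason nobody linked to the trial is coded as having had no SAE. The odds ratio then compares how often events were attributed to the trial, and a reader of the published table would take it for a comparison of risk.

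Attribution may also differ between arms. The exemption is worded by relation to a website that usual care does not receive; that arm gets brief online advice (protocol, Usual Care). The active arms are encouraged to do physical activity, strength and balance exercises (protocol, Active Lives). An assessor therefore has more to attribute an injury to in two arms than in the third. Conversely, a true excess of admissions that nobody connected with a website would hardly show. This regression is the only between-arm SAE analysis in the SAP.

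**Working it through.** **1. The passages side by side**

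| Step | SAP 4.7 | Protocol |
|---|---|---|
| Event definition | Any cause | Any cause |
| Event must be reported | Not stated | Only if judged related |
| Unrelated admission | Would need to be in the data | Exempt |
| Unrelated death | Would need to be in the data | End of Study form, not an SAE report |
| Relatedness summary | Implies both categories | Unrelated category would be largely empty |

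Since no SAE counts as expected, relatedness is the only filter on SAE reports.

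**2. Group size used below**

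The cognitive decline trial plans 3647 per arm. For 25% against 20%, 80% power and two-sided alpha 0.05, the pooled-variance formula gives n = (1.96·√(2·0.225·0.775) + 0.8416·√(0.1875 + 0.16))² / 0.05² = 1094. Then 2·1094/0.6 = 3646.7, which reproduces 3647. If notes were reviewed for 60% (assumption, borrowed from the plan's five-year follow-up figure), n = 3647·0.6 = 2188.

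**3. What the model would see if there were no true difference**

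The documents give no SAE rates and no attribution probabilities, so all rates here are assumptions. Reported rate r = p·a, where p is the true SAE rate and a is the proportion judged related. Odds ratio = [r1/(1−r1)] / [r0/(1−r0)]. With p = 20% in both arms and 3647 per arm:

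| a, usual care | a, active arm | Expected reports | Odds ratio | Rejection probability |
|---|---|---|---|---|
| 0.5% | 0.5% | 3.6 v 3.6 | 1.0 | nominal |
| 0.5% | 1% | 3.6 v 7.3 | 2.0 | about 20% |
| 0.5% | 2% | 3.6 v 14.6 | 4.0 | about 73% |
| 0.1% | 1% | 0.7 v 7.3 | 10.0 | about 64% |
| 1% | 0.5% | 7.3 v 3.6 | 0.5 | about 20% |

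For example, in the third row r0 = 0.20·0.005 = 0.001 and r1 = 0.20·0.02 = 0.004, giving 4.0. The odds ratio is close to a1/a0 whatever p is. Rejection probabilities use the normal approximation, which is rough at these counts.

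**4. What the model would miss**

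Take true rates of 20% and 23%, with attribution of 0.5% in both arms. Power = Φ[(d − 1.96·SE0)/SE1], with SE0 from the pooled rate and SE1 from the separate rates.
- All-cause events: 729 v 839 per arm, power about 88%.
- Related reports only: 0.10% v 0.115%, or 3.6 v 4.2 events per arm, power about 4%.

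**5. What notes review could detect**

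Smallest increase over the base rate with 80% power, from the same formula:

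| Base rate (assumed) | 3647 per arm | 2188 per arm |
|---|---|---|
| 10% | 2.1 points | 2.7 points |
| 15% | 2.4 points | 3.2 points |
| 20% | 2.7 points | 3.5 points |

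**The case against.** The strongest reply is that SAP 4.7 names no data source. An event that need not be reported may still be collected, and notes review captures deaths and hospital use. On that view the defect is an unstated source, and naming it would be enough. This stands in part: the SAP could be read that way. But nothing in the SAP links the notes-review data to section 4.7, and the protocol's SAE route as written delivers related events only.

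Four stronger readings are tempting, and the documents do not support them.
- *The assessor is unblinded.* SAP 2.3 lists participants, supporters and study team as unblinded. No passage says whether the site investigator is told the allocation. It is a reasonable inference, since judging relation to the website requires knowing who had it, but it is not stated.
- *The bias must run towards false harm.* The Causality section refers to research procedures in general. Usual care completes the cognitive tests and receives advice on activity and diet, so reports from that arm are possible.
- *Deaths are lost.* They are not: unrelated deaths reach the team, and SAP 4.5.11 analyses death regardless of cause.
- *The model will give an unbounded odds ratio.* That needs, for instance, 0.5% of all website-arm participants (about 18 of 3647) to have a related SAE and none in usual care. If 15% are admitted (547 per arm) and 0.5% of those admissions are judged related, about 2.7 reports are expected; 3 v 0 gives a Fisher p of 0.25, which is uninformative rather than alarming.

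It is also fair to say that no stated objective is a safety comparison and that no interim analysis or stopping rule uses SAEs. That limits the severity.

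**Conclusion.** The mismatch is real and can be read directly from the two documents. Applied to the reports the protocol requires, the regression in SAP 4.7 would treat unreported non-fatal SAEs, mainly admissions, as non-events and would estimate differences in attribution. Differential attribution is plausible because of the website wording, but its size and direction cannot be derived; the odds ratios above show only what assumed rates would produce. The firmer consequence is that true differences in all-cause admissions would go largely undetected by this analysis. The relatedness summary could still show grades of relatedness, but not a full comparison of related with unrelated events.

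This should be fixed before analysis. It is not critical: no primary or secondary effectiveness estimate depends on it, and all-cause death is already covered.

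**What to change.** 1. Reconcile SAP 4.7 with the protocol's Causality, exemptions and Reporting sections, and state the data source for each safety output.
2. List investigator-reported related SAEs descriptively by arm, without a comparative regression.
3. Make the between-arm safety comparison all-cause hospital admission, with A&E attendance, from the notes review in the three randomised arms. Report risk differences with 95% confidence intervals for each active arm against usual care, beside the death analysis in SAP 4.5.11. (The resource-use row of Table 2 is broken in the text available; its attendance item is read here as A&E.)
4. Say whether pre-planned admissions count, since the protocol does not class them as SAEs unless they are deemed related.
5. State the time window. The protocol's Health economic analysis section places notes review at both years 1 and 5, while the Table 2 footnote places it at one or the other. This decides whether the comparison can be made at one year.

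**Cost:** SAP wording and use of data already planned for extraction, plus a decision on notes-review timing. The comparison is limited to participants whose notes are reviewed, so the SAP should report that number by arm. The detectable differences in the working are for the cognitive decline trial.

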# 5 Tables, listings and figures templates

Table 1 – List of Measures

	Measure		Baseline Year 1 and Year 5 follow-up			Baseline Year 1 and Year 5 follow-up Year 2, year 3 an follow-up								rear 4
		Usual	Active Brains	AB + Support	Cohort group	Usual	Active Brains	AB + Support	Cohort group	Usual	Active Brains	AB + Support	Cohort group	
m birt expe	ient Socio Demographic leasures: (age, date of h, gender, postcode (to estimate deprivation indices); internet erience, education level, york status, ethnicity, height, weight)	Х	Х	Х	Х									
me med or stat	Clinical/behavioural easures collected from patient report: dealth conditions and dications, family history f dementia b, smoking cus, alcohol intake, BMI, cential dementia status.	X	X	X	X	X	X	X	X					
Se	If-reported respiratory infections					Х	Х	Х	Х					
СО	VID-19 and long-COVID status	Xc	Xc	Xc	Xc	Х	Х	Х	Х	Х	Х	Х	Х	
Out	t of pocket expenditure					Х	Х	Х	Х					
note	linical measures from es review (comorbidities, estolic blood pressure, olesterol, frailty score)					X*	X*	X*						
Cognitive Performance Tasks	Primary Outcome: Reasoning (measured using the Baddeley reasoning test)	Х	Х	Х	Х	Х	Х	Х	Х	X	Х	Х	Х	
Cognitive Perfo	Spatial Working Memory (measured using the Self ordered search test)	Х	Х	Х	Х	Х	Х	Х	Х	X	Х	Х	Х	

											•
neasured git' span	X	Х	Х	X	X	Х	Х	X	Х	Х	Х
easured paired	X	х	х	X	Х	х	х	X	Х	X	X
	Х	Х	Х	Х	Х	Х	Х	Х	Х	Х	Х
	Х	Х	Х	Х	Х	Х	Х	Х	Х	Х	Х
ment				Х	Х	Х	Х				
ire	Х	Х	Х	Х	Х	Х	Х	Х	Х	Х	Х
D) X	Х	Х	Х	Х	Х	X	Х	Χ	Х	Х	Χ
X	Х	Х	Х	Х	Х	Х	Х				
X	Х	Х	Х	Х	Х	Х	Х				
tia				Х*	Х*	X*					
				X*	X*	X*					
vill age as, E				X*	X*	X*					
isage				Х	Х	Х					
naire, f 2 items	Х	Х	Х	Х	X	X	Х	Х	X	Х	X
viours				Х	Х	Х	Х	Χ	Х	Х	Х
					Χ	Х	Х				
felt - ed with											
	Х	Х	Х	X 	X 	X 	X 				
rcise X	Х	Х	Х	Х	Х	X	Х				
ort X	Х	Х	Х	Х	Х	Х	Х				
	measured git' span )  rt-term	measured git' span )  rt-term easured paired earning)  f IQCODE X X X ment  cal X X X X X X X X X X X X X X X X X X X	measured git' span )  rt-term	neasured git' span )  rt-term	measured git' span )  ret-term	Treasured git'span	Interest   Interest	Tetterm	Measured git'span	Measured git's pan	measured git' span

Social Support for Exercise			1			Х	Х	Х				
scale						^						
Locus of Causation in	Х	Х	Х	Х	Х	Х	Х	Х				
Exercise												
Technology Acceptance						Х	Х	Х				
Model Perceived Ease of												
Use scale												
Pedometer use/purchase					Х	Х	Х	Х				
Objective patient data			•				•					
Usage of the Active Brains		Χ	Х	Х		Χ	Х	Х		Х	Х	Х
website throughout												
(including what components												
viewed and any data												
entered online such as at												
goal reviews).												
Objective supporter data								 	1			
Supporters' Usage of Active			Х				Х				Х	
Brains website (throughout												
study)												
Emails sent to participants			Х				Х				Х	
throughout study												
Qualitative data							_					
Interviews with patients					Xa	Xa	Xa	Xa				
about their experiences of												
the study and/or												
intervention												
Interviews with Central							Χ					
Support Facilitators about												
their experiences of the												
study and intervention												
Proxy-Measures (not cohort	group				1				1			
		В	aseline			Years	s 1 and 5			Yea	rs 2-4	
Informant Questionnaire on												
Cognitive Decline in the							Χ					
Elderly (IQCODE) (short												
form) [53]												
Quality of Life (EQ5D5L-												
proxy version 2) to be							Х					
completed by the												
nominated contact person												
(if necessary)												
IADL proxy version to be												
completed by the							Χ					
nominated contact person												
(if necessary)												

\*=notes a measure collected at notes review. ¹ = collected at year one only (not year five also)

<sup>a = process interviews to be conducted 2-12 months after commencement of study; b = baseline only; c = COVID-19 questions only (not long-COVID) at baseline

## **SAP** revision history

Version number	Revision history	Author	Date
